9.2.4 Regulatory Reporting Requirements for SAEs

- Prompt notification by the investigator to the Sponsor of SAEs is essential so that legal obligations and ethical responsibilities toward the safety of participants and the safety of a product under clinical investigation are met.
- An investigator who receives an investigator safety report describing SAEs or other specific safety information (eg, summary or listing of SAEs) from the Sponsor will file it along with the IB and will notify the IRB/ IEC, if appropriate according to local requirements.

Sponsor or designee will be reporting AEs to regulatory authorities and IECs according to local applicable laws, including European Directive 2001/20/EC and Food and Drug Administration Code of Federal Regulations 21 CFR Parts 312 and 320. A SUSAR is a subset of SAEs and will be reported to the appropriate regulatory authorities and investigators following local and global guidelines and requirements.

9.2.5 Pregnancy

In the event a participant becomes pregnant during the trial, the study treatment must be discontinued immediately. If the participant becomes pregnant during the study period until the end of study, the investigator must immediately notify the BMS Medical Monitor/designee of this event and complete and forward a Pregnancy Surveillance Form to BMS Designee within 24 hours of awareness of the event and in accordance with SAE reporting procedures described in [Appendix 3](#).

Protocol-required procedures for study discontinuation and follow-up must be performed on the participant.

Follow-up information regarding the course of the pregnancy, including perinatal and neonatal outcome and, where applicable, offspring information, must be reported on the Pregnancy Surveillance Form.

Any pregnancy that occurs in a female partner of a male study participant should be reported to the Sponsor or designee. In order for the Sponsor or designee to collect any pregnancy surveillance information from the female partner, the female partner must sign an informed consent form for disclosure of this information. Information on this pregnancy will be collected on the Pregnancy Surveillance Form.

9.2.6 Laboratory Test Result Abnormalities

The following laboratory test result abnormalities should be captured on the nonserious AE eCRF or SAE Report Form electronic, as appropriate. Paper forms are only intended as a back-up option when the electronic system is not functioning.

- Any laboratory test result that is clinically significant or meets the definition of an SAE
- Any laboratory test result abnormality that required the participant to have study treatment discontinued or interrupted
- Any laboratory test result abnormality that required the participant to receive specific corrective therapy

It is expected that wherever possible, the clinical rather than laboratory term would be used by the reporting investigator (eg, anemia vs low hemoglobin value).

9.2.7 Potential Drug-induced Liver Injury

Clinical chemistry and coagulation tests will be assessed as indicated in [Section 2](#) (Schedule of Activities). Participants with abnormal liver blood tests should be further assessed to determine if

these meet the criteria for discontinuation of the study treatment (see [Section 8.1](#) [Discontinuation From Study Treatment]) or the criteria for potential DILI.

Potential DILI is defined as:

- 1) Aminotransferase (ALT or AST) elevation $> 3 \times$ ULN,
AND
- 2) Total bilirubin $> 2 \times$ ULN, without initial findings of cholestasis (elevated serum alkaline phosphatase),
AND
- 3) No other immediately apparent possible causes of AT elevation and hyperbilirubinemia, including, but not limited to, viral hepatitis, pre-existing chronic or acute liver disease, or the administration of other drug(s) known to be hepatotoxic.

Identification of a clinically significant elevation(s) in liver-related chemistry or coagulation tests (including those defined in [Section 8.1](#) [Discontinuation From Study Treatment], or meeting the definition for potential DILI) should be followed by repeat testing of ALT, AST, total bilirubin, ALP, and INR within 48 to 72 hours to: (1) confirm the abnormalities, and (2) determine if they are increasing or decreasing.

Investigators must consult with the BMS Medical Monitor/designee immediately if a participant meets the laboratory criteria for potential DILI.

Investigators should consider gathering additional clinical information and laboratory and imaging tests to seek other possible causes of the observed liver blood test abnormalities, including (but not limited to) acute viral hepatitis, alcoholic and autoimmune hepatitis, biliary obstruction (small and large duct), cardiovascular causes (eg, ischemic hepatitis), nonalcoholic steatohepatitis, and the effect of concomitant treatments.

A review of all concomitant medications should include herbal medicines, dietary supplements, nonprescription OTC medications, including acetaminophen/paracetamol, and occupational exposure to chemical agents.

Wherever possible, timely confirmation of initial liver-related laboratory abnormalities should occur prior to the reporting of a potential DILI event. All occurrences of potential DILI, meeting the defined criteria must be reported as SAEs (see [Section 9.2](#) [Adverse Events] and [Appendix 3](#) for reporting details). All participants with clinically significant abnormalities in liver-related blood tests, or potential DILI, must be followed until all abnormalities return to normal or to the IM011077 study baseline state.

9.2.8 Adverse Events of Interest

All AEs and SAEs that arise in the study will be reported and investigated. However, because of the characteristics of the disease under study, and deucravacitinib in particular, some AEs are

considered AEs. AEs may be serious or nonserious. Such events may require further investigation to better characterize and understand them.

In the deucravacitinib clinical development program, certain skin-related AEs (eg, acne), infection AEs, and creatine kinase elevation have been identified as potential AEs. However, there has been no definitive assessment on the causal relationship between these events and treatment with deucravacitinib.

In addition, given that immunosuppression is consistent with the mechanism of action of deucravacitinib, malignancies are considered to be an important potential risk of therapy with deucravacitinib and will be monitored as AEs. Malignancies were not identified as adverse findings in nonclinical studies or in clinical studies of deucravacitinib.

Additional information on AEs will be collected in this study. Reporting of an AE or SAE that includes a Preferred Term that is linked to an AEI will trigger specialized eCRF pages to collect additional information related to characterization, social/family history, risk factors, signs/symptoms, diagnostics, and treatments. Additional information may also be requested to aid in the evaluation of these AEs.

9.2.9 Other Safety Considerations

Any significant worsening noted during interim or final physical examinations, ECG, x-ray filming, or any other potential safety assessment required or not required by protocol should also be recorded as a nonserious or serious AE, as appropriate, and reported accordingly.

9.3 Overdose

[REDACTED]

In the event of an overdose the investigator/treating physician should:

- 1) Contact the BMS Medical Monitor/designee immediately.
- 2) Closely monitor the participant for AEs/SAEs and laboratory abnormalities until deucravacitinib can no longer be detected systemically [REDACTED]
- 3) Document the quantity of the excess dose as well as the duration of the overdosing in the eCRF.

Decisions regarding study treatment interruptions or modifications will be made by the investigator in consultation with the BMS Medical Monitor/designee based on the clinical evaluation of the participant.

9.4 Safety

Planned time points for all safety assessments are listed in [Section 2](#) (Schedule of Activities). All urgent safety concerns must be discussed with the Sponsor immediately upon occurrence or awareness to determine if the participant should continue or discontinue study treatment.

Safety evaluations that will be performed in addition to AE monitoring are physical examinations (Section 9.4.2), vital signs (Section 9.4.3), ECGs (Section 9.4.4), laboratory tests (Section 9.4.5), TB screening (Section 9.4.6), and concomitant medication use (Section 7.7).

9.4.1 Preventative Care

Investigators are encouraged to ensure that participants are up-to-date with preventative care for IBD, based on local standard of care. This may include:

- Non-live vaccinations
 - Non-live vaccinations can be administered during the study (including SARS-CoV-2 messenger ribonucleic acid (mRNA) vaccines). The efficacy and safety of vaccines in participants receiving deucravacitinib have not been studied.
- Periodic surveillance for IBD associated colonic dysplasia or screening for colorectal carcinoma, based on local standard of care.
 - Biopsies collected for suspected colonic dysplasia should follow site-specific process for screening for colorectal carcinoma.
- Additional preventative care outlined in research society guidance (eg, American College of Gastroenterology guide).⁵⁵

9.4.2 Physical Examinations

Schedules for physical examinations are provided in the Section 2 (Schedule of Activities). Complete physical examinations should be performed by a medical doctor or someone who is authorized to perform the examinations by training and performs this task under the supervision of the investigator. Key aspects of the examination should evaluate important body systems, including skin, as clinically indicated. Every effort should be made to ensure the same evaluator will complete the examination for each participant at all visits throughout the study. Documentation of who performed the examination is to be recorded in source notes.

Significant findings should be recorded as AEs on the AE eCRF. AEs that are continuing from the parent study will be captured in both parent study and Study IM011077 databases.

Schedules for targeted physical examinations are provided in Section 2 (Schedule of Activities). The targeted physical examination will include (at a minimum) an abdominal examination, skin examination, and an examination of body systems with previously noted abnormalities and/or those body systems associated with any new complaints from the participant.

9.4.3 Vital Signs

Vital signs including body weight, body temperature, and seated blood pressure and heart rate will be obtained as indicated in Section 2 (Schedule of Activities) and recorded in the relevant eCRF. Seated blood pressure and heart rate should be measured after the participant has been resting quietly for at least 5 minutes. The Day 1 height measurement should not be collected. This height measurement should be carried over from the parent study screening visit and entered into Study IM011077 database (eg, eCRF).

9.4.4 **Electrocardiograms**

ECGs will be performed as indicated in [Section 2](#) (Schedule of Activities). ECGs will be read locally. Clinically significant ECG findings will be recorded in the relevant eCRF and should be discussed with the BMS Medical Monitor/designee. Any clinically significant ECG findings should be recorded on the appropriate AE page of the eCRF.

9.4.5 **Clinical Safety Laboratory Assessments**

Investigators must document their review of each laboratory safety report.

A central or local laboratory (where allowed by local laws, regulations, and guidance) will perform safety laboratory assessments (as indicated in operational documents; except urine pregnancy tests, which may be performed in clinic, as per local SOC) and provide reference ranges and laboratory reports.

Any laboratory test result that the investigator considers clinically relevant for safety is to be recorded on the appropriate AE eCRF.

The timing of laboratory assessments is indicated in [Section 2](#) (Schedule of Activities).

The laboratory parameters to be assessed for clinical safety throughout the study are listed in [Table 9.4.5-1](#).

Table 9.4.5-1: Summary of Laboratory Parameters Used to Assess Clinical Safety

Hematology	
Hemoglobin Hematocrit Iron Ferritin Total iron-binding capacity (TIBC) Total leukocyte count, including absolute neutrophil count (ANC) and absolute lymphocyte count	Platelet count Red blood cell (RBC) count Complete blood count (CBC) differential (manual separate smear preferred; automatic differential acceptable when manual is not available); must include MCV, MCHC, MCH
Chemistry	
Aspartate aminotransferase (AST) Alanine aminotransferase (ALT) Gamma glutamyltransferase (GGT) Total bilirubin Direct bilirubin Alkaline phosphatase (ALP) Lactate dehydrogenase (LDH) Creatinine Blood urea nitrogen (BUN) Uric acid Total protein Albumin Sodium	Potassium Chloride Calcium Phosphorus Magnesium Creatine kinase Performed after ≥ 10-hour fast at annual visits (Weeks 48, 96, 144, 192, 240, and 288): Fasting lipid panel (total cholesterol, high-density lipoprotein cholesterol, low-density lipoprotein cholesterol, and triglycerides) Fasting glucose
Coagulation	
Prothrombin time (PT) International normalized ratio (INR)	Either partial thromboplastin time or activated partial thromboplastin time (aPTT)

Table 9.4.5-1: Summary of Laboratory Parameters Used to Assess Clinical Safety

Urinalysis	
Protein Glucose Blood Leukocyte esterase Specific gravity pH	Microscopic examination of the sediment if blood, protein, or leukocyte esterase are positive on the dipstick 
 Spot urine will be assessed for urine protein and urine creatinine
Other Analyses	

 Follicle-stimulating hormone: to confirm postmenopausal status in females (refer to Appendix 4) Urine and/or serum pregnancy testing (β-hCG): performed for WOCBP 	
Stool Tests (to be performed when deemed appropriate by investigator)	

 Stool culture: culture for potentially pathogenic enteric bacteria, including (but not limited to) Salmonella, Shigella, Campylobacter, and enterohemorrhagic Escherichia coli. Testing for additional enteric pathogens, including bacteria, protozoa, ova, and parasites, may be performed based on the investigator’s clinical judgment. Stool for Clostridioides (formerly Clostridium) difficile testing: stool for C. difficile Toxin A and B test (EIA) and GDH antigen test (EIA), with reflex to NAAT (C. difficile polymerase chain reaction) if either positive. 	

Abbreviations: [REDACTED] β -hCG = beta-human chorionic gonadotropin; [REDACTED] EIA = enzyme-linked immunosorbent assay; GDH = glutamate dehydrogenase; [REDACTED] MCH = mean corpuscular hemoglobin; MCHC = mean corpuscular hemoglobin concentration; MCV = mean corpuscular volume; NAAT = nucleic acid amplification test; WOCBP = women of childbearing potential.

9.4.6 Tuberculosis Screening

In order to be eligible for the study, a participant must not have symptoms or signs of active TB, as judged by the investigator.

Evidence of active or latent TB includes:

- History of active TB prior to the Day 1 visit of this study (IM011077); or
- Signs or symptoms of active TB as judged by the investigator; or
- A chest x-ray obtained anytime within [REDACTED] prior to Day 1 of this study, with documentation, and evidence of current active or old active pulmonary TB; or

[REDACTED]

[REDACTED]

Prior to receiving the first dose of study treatment in this study and approximately every year, participants should be assessed using the Tuberculosis Risk Assessment Tool (refer to [Appendix 5](#)).

A participant with a negative QuantiFERON or T-Spot test may be eligible to participate in the study provided he/she does not have any clinical or radiologic evidence supporting a diagnosis of active TB or LTBI.

A participant with an indeterminate QuantiFERON test or a borderline T-Spot test must have a retest before he/she is eligible to participate in the study. If the second result is again indeterminate or borderline, the participant will be excluded from the study. If the second result is negative, the participant may be eligible provided there is no clinical or radiologic suspicion of active TB or LTBI.

A participant diagnosed with LTBI at the end of treatment visit of the parent study should be referred to an appropriate specialist for consideration for prophylactic treatment for LTBI, per local guidelines.

9.4.7 Imaging Safety Assessment

Please refer to [Section 9.4.1](#) for periodic surveillance (including study-related endoscopy) for IBD associated colonic dysplasia or screening for colorectal carcinoma.

9.5 Pharmacokinetics

The PK of deucravacitinib and metabolites (if applicable) will be derived from plasma concentration vs time data. The trough observed plasma concentration (C_{trough}) will be summarized as part of the PK parameters summary.

The plasma samples will be analyzed for deucravacitinib and metabolites (if applicable) by a validated liquid chromatography tandem mass spectrometry assay. In addition, plasma samples will be archived for potential analysis of other analytes, if the need arises and to the extent possible. Detailed instructions for the PK blood collection, labeling, processing, storage, and shipping will be provided to the site in the Laboratory Manual.

The sampling schedule for the assessment of PK and PD is provided in [Table 9.5-1](#).

Table 9.5-1: Pharmacokinetic Sampling Schedule for All Participants (Study IM011077)

Study Day of Sample Collection Visit window (± 14 days)	Event	Time Relative to Deucravacitinib Dose ^a (hr:min)	Deucravacitinib PK Plasma Sample
Day 1	Predose ^b	00:00	X
Day 169 (Year 1, Week 24)	Predose ^c	00:00	X
Day 337 (Year 1, Week 48)	Predose ^c	00:00	X
Day 505 (Year 2, Week 72)	Predose ^c	00:00	X
Day 673 (Year 2, Week 96)	Predose ^c	00:00	X
Day 841 (Year 3, Week 120)	Predose ^c	00:00	X
Day 1009 (Year 3, Week 144)	Predose ^c	00:00	X
Day 1177 (Year 4, Week 168)	Predose ^c	00:00	X
Day 1345 (Year 4, Week 192)	Predose ^c	00:00	X
Day 1513 (Year 5, Week 216)	Predose ^c	00:00	X
Day 1681 (Year 5, Week 240)	Predose ^c	00:00	X
Day 1849 (Year 6, Week 264)	Predose ^c	00:00	X
Day 2017 (Year 6, Week 288)	Predose ^c	00:00	X
End of Treatment/Early Termination			X

Abbreviations: hr = hour; min = minute; PK = pharmacokinetic.

- ^a PK sample is expected to be collected as close to the planned time as operationally feasible and always records the exact PK collection date and time.
- ^b The Day 1 pre-dose sample must be drawn before the morning dose of study treatment on the visit date. The post-PK dose of study treatment should be taken at the site from Study IM011077.
- ^c Pre-dose samples must be drawn before the morning dose of study treatment on the visit day; at these visits, study treatment will be taken at the site.

9.7 Pharmacogenomics

Not applicable.

[REDACTED]

[figure not shown]
[REDACTED]

[figure not shown]
[REDACTED]

[figure not shown]
[REDACTED]

[figure not shown]
[REDACTED]

[REDACTED]

9.9 Health Economics OR Medical Resource Utilization and Health Economics

Medical resource utilization and health economics data associated with medical encounters (disease-related healthcare utilization) will be collected in the eCRF by the investigator and study-site personnel for all participants throughout the study. This instrument provides questions/prompts representative of the data to be collected through eCRF [REDACTED] Protocol-mandated procedures, tests, and encounters are excluded. [REDACTED]

9.10 Electronic Informed Consent

Where applicable according to regional, local, and institutional regulations, sites may opt to use electronic informed consent (eConsent). eConsent uses digital technology to provide interactive tools for obtaining informed consent. IRBs/IECs should review the content of any multimedia components prior to launch of the digital platform as part of the informed consent review process.

Participants will be provided with a printed copy of the eConsent. In some cases, depending on local regulations, the multimedia components may be delivered electronically, whereas signatures will be collected on paper. Paper informed consent forms will be available in the event the regulations do not allow the use of eConsent and to allow both options for participants and sites.

10 STATISTICAL CONSIDERATIONS

10.1 Sample Size Determination

Because this uncontrolled, open-label, long-term extension study is for observational purposes only, no formal calculations of sample size and power determination will be made. All qualified participants who complete the final treatment visit from an applicable parent study will be eligible to participate. Approximately 300 participants are expected to roll over into this study from the parent studies.

10.2 Populations for Analyses

For purposes of analysis, the following populations are defined:

Population	Description
Enrolled Population	All participants who sign informed consent for entry into Study IM011077.
As-treated	All enrolled participants who took at least 1 dose of study treatment in Study IM011077.
Biomarker Population	All participants who receive at least 1 dose of study treatment in Study IM011077 and have at least 1 post-treatment biomarker measurement.
PK Population	All participants who receive at least 1 dose of study treatment in Study IM011077 and have any available concentration-time data.

Abbreviation: PK = pharmacokinetic.

10.3 Endpoints

10.3.1 Primary Endpoints

The primary objective of this study is to assess the safety and tolerability of long-term use of deucravacitinib in participants with moderate to severe CD or moderate to severe UC. To support this objective, the following endpoints will be assessed:

- Number and proportion of participants experiencing AEs, SAEs, AEs leading to study discontinuation, and AEs.
- Number and proportion of participants experiencing abnormalities in laboratory testing, ECG, and vital sign parameters over time.
- Changes from IM011077 study baseline for laboratory testing, ECG, and vital signs.

[REDACTED]

[REDACTED]

[REDACTED]

[REDACTED]

[REDACTED]

[REDACTED]

[REDACTED]

[REDACTED]

[REDACTED]

[REDACTED]

[REDACTED]

[REDACTED]

[REDACTED]

[REDACTED]

[REDACTED]

[REDACTED]

[REDACTED]

[REDACTED]

[REDACTED]

[REDACTED]

[figure not shown]
[REDACTED]

[figure not shown]
[REDACTED]

[REDACTED]

[REDACTED]

[REDACTED]

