10.4 Statistical Analyses

10.4.1 Efficacy Analyses

Because this study is for observational purposes, no statistical tests for treatment comparisons will be conducted. Categorical data will be summarized as frequency counts and percentages. Continuous data will be summarized using number of participants (n), mean, standard deviation (SD), median, minimum, and maximum unless otherwise specified. Efficacy variables will be summarized for all visits in which the variable is assessed. Complete details of the planned analyses will be documented in the SAP and finalized before database lock. Summaries will be provided for the As-treated population. Participants will be summarized according to the treatment they received in their parent trial.

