10.4.2 Safety Analyses

Safety data will be analyzed for AEs, SAEs, laboratory analytes, and vital signs. Safety will be summarized using the As-treated population. Participants will be summarized according to the treatment they received in their parent trial, as well as by indication and overall. Categorical data will be summarized as frequency counts and percentages. Continuous data will be summarized using n, mean, SD, median, minimum, and maximum unless otherwise specified.

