10.4.2.1 Adverse Events

AEs for this study will be collected from the time the participant signs the informed consent form until the Final Safety Visit (ie, 28 days after EOT or ET) at the timepoints specified in [Section 2](#) (Schedule of Activities). AEs that are ongoing from parent studies that worsen after the participant signs the informed consent form will be reported as new AEs in Study IM011077. AEs reported during parent studies that have either resolved or are ongoing [REDACTED] from the parent study end of treatment visit will be recorded as Medical History in Study IM011077.

TEAEs are events that occur after the administration of the first dose of study treatment in Study IM011077. AEs that were ongoing during the parent study and worsen once study treatment is initiated in this study will also be considered treatment emergent. All AEs will be coded using the Medical Dictionary for Regulatory Activities (MedDRA) and presented by System Organ Class and Preferred Term. Serious AEs and deaths, AEs leading to study treatment discontinuation, AEs by maximum severity, and AEs by relationship will also be summarized by the MedDRA System Organ Class and Preferred Term. All TEAEs will also be summarized by Preferred Term sorted by decreasing frequency.

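### AEs are to be reported as n (%) only, with no exposure-adjusted or by-period summary, so the named tables cannot show whether risk changes over up to 288 weeks

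*Combined protocol and SAP*

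**What the plan says.** Section 10.3.1 states the aim: "The primary objective of this study is to assess the safety and tolerability of long-term use of deucravacitinib". The AE endpoint that supports it is "Number and proportion of participants experiencing AEs, SAEs, AEs leading to study discontinuation, and AEs". The final term there reads AEIs (adverse events of interest) in the synopsis and in Table 4-2; the slip does not affect this point.

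Section 10.4.2 gives the method: "Safety will be summarized using the As-treated population", and "Categorical data will be summarized as frequency counts and percentages". The columns are fixed by "Participants will be summarized according to the treatment they received in their parent trial, as well as by indication and overall". No column or row is a time period.

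Section 10.4.2.1 sets the collection window, "AEs for this study will be collected from the time the participant signs the informed consent form until the Final Safety Visit", and lists the tables: System Organ Class and Preferred Term, SAEs and deaths, AEs leading to treatment discontinuation, maximum severity and relationship. It ends with "All TEAEs will also be summarized by Preferred Term sorted by decreasing frequency". None uses person-time, incidence rates, time to event or study periods. In 10.3.1 the qualifier about time is attached to laboratory, ECG and vital-sign abnormalities, not to AEs.

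Further detail is deferred. Section 10.4.1 says "Complete details of the planned analyses will be documented in the SAP and finalized before database lock", and 10.4.3 and 10.4.4 also point to the SAP. No SAP text was available for this review.

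**The concern.** Time at risk will differ widely. Treatment can run to Week 288 (5.1), but it may end at any time (5.1.3), must end for treatment failure and for AE and laboratory triggers (8.1), and participants are not replaced (8.4). Someone who stops leaves AE collection about 28 days later (8.1.2, 9.2.1). A single percentage of treated participants therefore depends on how risky the drug is and also on how long people stayed.

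It also carries no timing. Ten events in the first year and ten in the sixth give the same entry in the table, yet for a study of long-term use these are different findings. This matters most for less common events, namely SAEs and AEIs such as infection and malignancy; section 9.2.8 calls malignancy an important potential risk. It matters little for very common AEs, where nearly everyone has an event under any pattern.

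If an interim analysis is done (10.4.4 says only that one may be), participants are also cut off at different lengths of follow-up, and the percentage no longer refers to Week 288.

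**Working it through.** The plan has no figure to reproduce: 10.1 disclaims any sample-size calculation and gives no event or discontinuation rate.

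**Inputs from the protocol.** N is about 300 (10.1), treatment lasts 288 weeks (5.1) and follow-up 28 days (5.1.3, 8.1.2). So T = 288 × 7 / 365.25 = 5.52 years and L = 28 / 365.25 = 0.077 years.

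**Assumed inputs.** Annual discontinuation p is 10%, 15% or 30%, giving a hazard d = −ln(1 − p). All event rates are assumed.

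**Check 1: can n (%) show a change in risk?** Two patterns are compared: a flat 3 per 100 PY, and a rate stepping up 1, 2, 3, 4, 5, 6 per 100 PY over six 48-week periods. The expected proportion is the integral of r(t)S(t) from 0 to T + L, with S(t) = exp(−d·max(t − L, 0))·exp(−H(t)), where H is the cumulative event hazard. The last rate is held through the 28-day tail.

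| Annual discontinuation | Flat: n (%) | Rising: n (%) | Overall rate per 100 PY, flat vs rising |
|---|---|---|---|
| 10% | 35.6 (11.9%) | 38.0 (12.7%) | 3.00 vs 3.16 |
| 15% | 31.2 (10.4%) | 31.8 (10.6%) | 3.00 vs 3.01 |
| 30% | 21.2 (7.1%) | 18.3 (6.1%) | 3.00 vs 2.55 |

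A sixfold rise moves the count by at most about 3 of 300, and the difference changes sign. The overall exposure-adjusted rate is nearly as blind. By-period rates would read 3.0 throughout against 1.0 to 6.0.

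A second calculation, with other patterns and 10% dropout per 48-week year, agrees. Constant (2.40 per 100 study-years), rising (0.67 to 4.68) and falling (3.81 to 0.54) hazards can all give 30 of 300.

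**Check 2: how far does retention alone move n (%)?** For a constant hazard r, P₀ = r/(r + d) × (1 − exp(−(r + d)T)), and the crude proportion is P = 1 − exp(−rL)(1 − P₀).

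- At r = 0.05 and p = 15%: d = 0.1625, P₀ = 0.05/0.2125 × (1 − exp(−1.173)) = 0.1625, and P = 1 − 0.9962 × 0.8375 = 16.6%.
- At p = 10% the same formula gives 18.8%, and at 30% it gives 11.3%. The ratios are 1.14 (10% vs 15%) and 1.66 (10% vs 30%).
- At r = 1.5 (very common AEs) the values are 94.1%, 91.3% and 82.9%, with ratios of only 1.03 and 1.14.

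Nothing in the documents suggests that columns will differ as much as 10% vs 30%.

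**Check 3: what precision would by-period rates have?** In the last 48-week period (with the tail), overall:

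| Annual discontinuation | PY (approx.) | Expected events, flat vs rising |
|---|---|---|
| 10% | 151 | 4.5 vs 9.0 |
| 15% | 114 | 3.4 vs 6.7 |
| 30% | 43 | 1.3 vs 2.6 |

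An even split by indication (assumed) at 15% leaves about 57 PY and 1.7 vs 3.4 events per indication, which is mostly noise.

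Pooled to 96-week blocks at 15%, the rising pattern has 477.7, 338.8 and 239.3 PY and rates of about 1.5, 3.5 and 5.5 per 100 PY. Exact Poisson 95% CIs, at the rounded expected counts of 7, 12 and 13 events, are 0.6 to 3.0, 1.8 to 6.2 and 2.9 to 9.3. At 30%, the first and last blocks overlap widely (0.5 to 3.2 and 1.6 to 11.6).

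**The case against.** The strongest objection is that the SAP is the usual place for such tables, it was not available, and nothing in the protocol rules them out. That stands as a limit: the point concerns what the protocol states and is not evidence that the SAP lacks these summaries. The deferrals sit under efficacy, other and interim analyses, and the safety sections contain none of their own. If the SAP has the tables, one confirming sentence closes the matter.

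A second objection is that this is an uncontrolled, descriptive study, that n (%) is a legitimate summary, and that preferring rates is a matter of taste. The first two parts are right. The third is not, because the stated objective concerns long-term use and the stated summary cannot speak to change over time.

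Third, an overall exposure-adjusted rate does not reveal timing. This is correct: it addresses unequal follow-up only, and the by-period display is needed for the rest.

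Fourth, by-period rates are weak at this size. In simulation with the sixfold rise, the first and last 96-week CIs separate in roughly 58%, 47% and 21% of trials at 10%, 15% and 30% discontinuation. For an assumed doubling from 2 to 4 per 100 PY they separate in about 5%, 4% and 2%. The display is therefore descriptive and should not be read as a test.

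Fifth, a clock starting at the first IM011077 dose ignores parent-study exposure, which differs: 52 plus 52 weeks in two parent studies and 12 plus 40 in the third (3.2). This stands as a caveat on what the periods mean.

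Finally, regular DMC review of AEs, SAEs and AEIs (5.1.5) helps protect participants during the study but does not specify final reporting.

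**Conclusion.** The concern holds as a cheap improvement; it is not an error. No planned table is wrong, and the crude percentage is valid as on-treatment cumulative incidence with discontinuation as a competing event. The AE summaries named in the protocol nevertheless cannot distinguish a flat risk from one that rises sixfold (a difference of at most about 3 of 300 participants in the cases tried), and they move with retention when risk does not. The size in this trial is unknown, because every event and discontinuation rate used here is an assumption. The effect is material for less common events and small for very common ones. Confidence is medium, mainly because the SAP may already supply what is missing.

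**What to change.** In 10.4.2.1 or the SAP, keep n (%) and add the following.

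- **Rates.** Person-years and first-event incidence per 100 PY with exact Poisson 95% CIs, for AEs, SAEs, AEs leading to treatment discontinuation and each AEI, overall, by indication and by parent treatment.
- **By period.** The same rates by 48-week period, with numbers at risk and PY, in the overall column only (by indication only where events allow), pooled to 96-week blocks where events are few.
- **Time at risk.** From the first IM011077 dose to the earliest of the first event, the Final Safety Visit (or last dose plus 28 days if that visit is missed), last contact or data cutoff. Keep time off drug during interruptions in the denominator, and say so.
- **Later events.** List related SAEs reported after that window separately and leave them out of the rates.

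The cost is wording, some programming and a few tables from dosing, visit and AE dates already collected, with no extra participants or visits. The limits to state are wide late-period CIs, a hazard assumed roughly constant within each period, no correction for informative discontinuation, and a clock that omits parent-study exposure.
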